## 15.3. EXPLORATORY EFFICACY

### 15.3.1. EXPLORATORY EFFICACY VARIABLES & DERIVATIONS

#### 15.3.1.1. Hamilton Anxiety Rating Scale

The Hamilton Anxiety Rating Scale (HAM-A) consists of 14 items. Each item is rated on a scale of 0 (feeling not present) to 4 (very severe prevalence of the feeling). The HAM-A total score is the sum of the 14 items and the score ranges from 0 to 56.

#### 15.3.1.2. Pain Question

The Pain question is a single item which assesses the average pain over the last 24 hours. The response is scored from 0 (no pain) to 10 (pain as severe as you can imagine).

---

Document:	C:\Users\q718413\Documents\NEP-MDD-201_SAP_v1.0_Final_06Dec2018.docx		
Author:	[name]	Version Number:	1.0
		Version Date:	06Dec2018

Template No: CS\_TP\_BS016 Revision 4  
Effective Date: 01Apr2016

Reference: CS\_WI\_BS005

Copyright © 2009, 2010, 2012, 2016 Quintiles Transnational Corp. All rights reserved.  
The contents of this document are confidential and proprietary to Quintiles Transnational Corp. Unauthorized use, disclosure or reproduction is strictly prohibited.

**Analysis Plan**

---

**15.3.1.3. Nonpharmacogenetic Biomarkers**

Results for the following nonpharmacogenetic biomarkers will be available: plasma nociception, serum IL-1 $\beta$ , IL-2, IL-6, IL-10, TNF $\alpha$ , IFN $\gamma$  and CRP. If applicable biomarker results below the limit of quantification (BLOQ) will be imputed as BLOQ/2 and biomarker results above the limit of quantification (ALOQ) will be imputed as the ALOQ for the purpose of change from baseline calculations.

**15.3.2. MISSING DATA METHODS FOR EXPLORATORY EFFICACY VARIABLE(S)**

No missing data imputation will be used for the exploratory efficacy variables.

**15.3.3. ANALYSIS OF EXPLORATORY EFFICACY VARIABLES**

**15.3.3.1. Hamilton Anxiety Rating Scale**

The change from baseline for the HAM-A total score to week 8 will be analyzed using the same method as the primary efficacy endpoint, substituting the baseline HAM-A total score as the covariate in place of the MADRS total score. Using the same model, the difference in between treatment groups will also be presented for the change from baseline to week 4. The HAM-A total score and change from baseline in HAM-A total score will be summarized through descriptive statistics by treatment group and visit.

**15.3.3.2. Pain Question**

The change from baseline for the Pain score to week 8 will be analyzed using the same method as the primary efficacy endpoint, substituting the baseline Pain score as the covariate in place of the MADRS total score. The Pain score and change from baseline in Pain score will be summarized through descriptive statistics by treatment group and visit.

**15.3.3.3. Nonpharmacogenetic Biomarkers**

The change from baseline to week 8 for each nonpharmacogenetic biomarker will be analyzed using an ANCOVA model with treatment group and investigative site as fixed effects and baseline biomarker result as a continuous covariate. The change from baseline in nonpharmacogenetic biomarker result will be summarized through descriptive statistics by biomarker, treatment group and visit. The number and percentage of BLOQ/ALOQ results at each visit will also be presented. In addition, panel plots displaying the correlation of the change from baseline to week 8 in biomarker level with the change from baseline to week 8 in MADRS total score and total treatment exposure will be presented.

**15.3.4. SUBGROUP ANALYSIS**

Analysis by the subgroups defined in [section 7.5](#) will be performed on efficacy endpoints according to the following table. The change from baseline to week 8 for each endpoint will be analyzed using the same method as the endpoint in the main analysis. For the anhedonia severity subgroup analysis, that term will be dropped from the model.

---

Document:	C:\Users\q718413\Documents\NEP-MDD-201_SAP_v1.0_Final_06Dec2018.docx		
Author:	[name]	Version Number:	1.0
		Version Date:	06Dec2018
Template No:	CS_TP_BS016 Revision 4	Reference:	CS_WI_BS005
Effective Date:	01Apr2016		

Copyright © 2009, 2010, 2012, 2016 Quintiles Transnational Corp. All rights reserved.  
The contents of this document are confidential and proprietary to Quintiles Transnational Corp. Unauthorized use, disclosure or reproduction is strictly prohibited.

Analysis Plan

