#### 15.2.1.9. Probabilistic Reward Task

The PRT is a measure of reward learning consisting of trials in which patients are asked to respond to two hardly distinguishable cues, of which one is more frequently rewarded. Patients complete a total 300 trials in 3 blocks of 100. Response bias for the rewarded category is the main outcome of interest (Pizzagalli, et al, 2008). In addition, the following outcome measures will be provided:

- Discriminability (subject's ability to differentiate between the two cues)
- Reaction time
- Accuracy (hit rates)

All measures will be computed and provided by the vendor in the source data for each block and as an overall total. The response bias and discriminability measures will also have log-linear adjusted values provided. The adjusted values for response bias and discriminability and original values for reaction time and hit rates at each block will be utilized in the analyses.

Additionally, there will be a series of checks on the data to insure validity of the data used in the analysis. Only subjects with data meeting the following criteria will be used in the analysis.

- The number of valid trials is >80% for each block
- Reward ratio of rich:lean is greater than 25:10 (ratio: 2.5) in each block.
- The number of rich rewards is between 24 and 30, inclusively.
- The number of lean rewards is between 7 and 10, inclusively.
- The lean accuracy in each block is greater than or equal to 40%.
- The rich accuracy in each block is greater than or equal to 40%.
- For combination of blocks e.g. Main, Total: If one block is not usable, then the combo is not usable (i.e. if block 2 is not usable, then total is not usable).

---

Document:	C:\Users\q718413\Documents\NEP-MDD-201_SAP_v1.0_Final_06Dec2018.docx		
Author:	[name]	Version Number:	1.0
		Version Date:	06Dec2018

Template No: CS\_TP\_BS016 Revision 4  
Effective Date: 01Apr2016

Reference: CS\_WI\_BS005

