15.2.3.9. Probabilistic Reward Task

Each outcome measure of the PRT will be summarized (mean, standard deviation, median, and range) at each visit. Response bias and discriminability will be summarized by block and treatment. Reaction time and hit rates will be summarized by stimulus (rich vs. lean), block and treatment. Line plots of means (+/-SD) will also be presented by treatment group and visit.

At each scheduled visit, an ANOVA model will be used to compare treatment groups. The models for response bias and discriminability will include terms for treatment, block, and treatment-by-block will be used to analyze treatment differences. The models for reaction time and hit rates will include terms for treatment, block, stimulus, and treatment-by-block will be used to analyze treatment differences. The models LS Means and standard errors (SEs) will be presented for each treatment group. The difference in LS Means with corresponding SEs, 95% confidence intervals for differences, and p-values will also be presented. No adjustments will be made for multiple comparisons.

All data, including the overall total scores, will be listed by treatment and patient.

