15.2.3.10. Effort Expenditure for Reward Task

Each outcome measure of the EEfRT will be summarized (mean, standard deviation, median, and

---

Document:	C:\Users\q718413\Documents\NEP-MDD-201_SAP_v1.0_Final_06Dec2018.docx		
Author:	[name]	Version Number:	1.0
		Version Date:	06Dec2018

Template No: CS\_TP\_BS016 Revision 4  
Effective Date: 01Apr2016

Reference: CS\_WI\_BS005

Analysis Plan

---

range) by treatment group at each visit. Line plots of means (+/-SD) will also be presented by treatment group and visit.

The analysis of completion rates will use an ANOVA model with a term for treatment to analyze treatment differences at each scheduled visit. The models LS Means and standard errors (SEs) will be presented for each treatment group. The difference in LS Means with corresponding SEs, 95% confidence intervals for differences, and p-values will also be presented. No adjustments will be made for multiple comparisons.

The analysis of preference will be completed utilizing Generalized Estimating Equation (GEE) models. A binary logistic distribution will be used to model the dichotomous outcome of preference at each scheduled visit. At each visit a series of models using a variety of factors will be fit. All models in the series will include explanatory variables reward magnitude, reward probability, and expected value (reward magnitude X probability) as a base. For each series, four models will be fit. The first will include the base variables with the additional variable of interest with no interactions. The next three models will include the same but with an interaction term between the variable of interest and each base variable in order. The variables of interest that will be explored include:

- Age
- Sex
- Treatment
- MADRS Total Score
- SHAPS Score (0 – 14 scoring method)
- DARS Total Score

The parameter estimates, standard error, 95% confidence interval, degrees of freedom and p-values will be presented to for each model.

All data will be listed by treatment and patient.

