**Subgroup Analyses for Efficacy Endpoints**

Efficacy Endpoint	Subgroup			
	Gender	Anhedonia Severity (SHAPS)		Baseline HAM-A (<20, >=20)
		(<=4, >4)	(<=7, >7)	
MADRS total score	X	X	X	X
PRT			X	
EEfRT			X	

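### The subgroup rule in SAP 15.3.4 conflicts with the main PRT and EEfRT analyses and cannot be applied to EEfRT preference

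*SAP*

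**What the plan says.** SAP 15.3.4 governs every cell of the table that follows it, headed "Subgroup Analyses for Efficacy Endpoints". Its rule is: "The change from baseline to week 8 for each endpoint will be analyzed using the same method as the endpoint in the main analysis". The table has three rows. MADRS total score is marked for all four subgroup splits; PRT and EEfRT are each marked only for the SHAPS split at 7. The paragraph then adds: "For the anhedonia severity subgroup analysis, that term will be dropped from the model".

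The main analyses to which the rule points are these:

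- **MADRS (SAP 15.1.1 and 15.1.3):** an MMRM of change from baseline, with baseline as covariate and a Week 8 contrast.
- **PRT (SAP 15.2.3.9):** "At each scheduled visit, an ANOVA model will be used to compare treatment groups". On terms: "The models for response bias and discriminability will include terms for treatment, block, and treatment-by-block". Reaction time and hit rates also have a stimulus term. SAP 15.2.1.9 says that per-block values are analysed.
- **EEfRT completion (SAP 15.2.3.10):** "The analysis of completion rates will use an ANOVA model with a term for treatment to analyze treatment differences at each scheduled visit".
- **EEfRT preference (SAP 15.2.3.10):** a series of GEE models of the hard-or-easy choice. "A binary logistic distribution will be used to model the dichotomous outcome of preference at each scheduled visit".

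**The concern.** The rule fixes the outcome and the method together, and for the reward tasks they do not match. For PRT and completion, a programmer must either apply the stated outcome in a model that the main analysis never fits, or repeat the main analysis and ignore the stated outcome. For preference, only the second course is open. The protocol does not settle it, because section 13.2.8.3 leaves the PRT and EEfRT details to the SAP.

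The choice can affect the result. Randomization is stratified at SHAPS 4 (protocol 10.3), not at 7, so stratification does not balance the arms within the groups used for these tasks. With a chance baseline difference between arms, the change score and the Week 8 value can give different answers. Anhedonia and task performance are both secondary objectives, and a choice left open until after unblinding is avoidable flexibility.

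**Working it through.** **The plan's own figure.** Protocol 13.1 gives 75% power for 44 per group, effect size 0.5, two-sided alpha 0.10 and a two-sample t-test. With df = 2 × 44 − 2 = 86 and noncentrality 0.5 × √(44/2) = 2.345, the noncentral t gives 0.752. The figure reproduces, but it concerns MADRS and the point does not depend on it.

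**Can the rule be run for each outcome?**

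- *MADRS:* yes. The main analysis already uses change.
- *PRT and EEfRT completion:* yes, but with a different response. SAP 6.6 defines change for quantitative measurements, and these qualify. A test fit of the treatment, block and treatment-by-block model to simulated PRT-shaped data (44 patients, three blocks) had full rank (2 × 3 = 6) with either the Week 8 value or the change score.
- *EEfRT preference:* no. Each trial yields 0 or 1. Even if trials could be paired across visits, the difference would be −1, 0 or 1, which a binary logistic model cannot take as its outcome.

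**What the choice of response does to precision.** Assume equal variance at baseline and Week 8, scaled to 1, and correlation r between them. The documents give no r, so a range is shown.

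- Week 8 value: variance 1.
- Change: 2(1 − r).
- Week 8 value adjusted for baseline: 1 − r², ignoring the one degree of freedom spent.
- Change relative to adjusted value: 2(1 − r)/(1 − r²) = 2/(1 + r).

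| r (assumed) | Change ÷ value | Adjusted ÷ value | Change ÷ adjusted |
|---|---|---|---|
| 0.2 | 1.6 | 0.96 | 1.67 |
| 0.3 | 1.4 | 0.91 | 1.54 |
| 0.5 | 1.0 | 0.75 | 1.33 |
| 0.7 | 0.6 | 0.51 | 1.18 |

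Against the planned visit value, change is less precise below r = 0.5, equal at 0.5 and more precise above it. Against a baseline-adjusted value, it is less precise at every r shown.

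**The same in power.** Assume 22 per arm in a subgroup (half of 44), a true effect of 0.5 SD of the visit value, and two-sided alpha 0.10. For change, the effect size becomes 0.5/√(2(1 − r)). Power on the Week 8 value is 0.495. On change it is 0.363, 0.396, 0.495 and 0.678 for r = 0.2, 0.3, 0.5 and 0.7.

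**The term to be dropped.** No anhedonia-severity term appears in the covariate list (SAP 7.1) or in the MADRS, PRT or completion models (15.1.3, 15.2.3.9, 15.2.3.10). SHAPS score enters only as one variable of interest in the preference GEE series.

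**The case against.** The strongest reply is that this is a wording slip in exploratory work. Protocol 13.2.12 calls all subgroup analyses exploratory, SAP 7.5 disclaims high power within subgroups, and no decision rule depends on them. That stands and limits the severity.

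Four stronger conclusions that a reader might draw are not supported:

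- *That the PRT and EEfRT rows cannot be run at all.* PRT measures and completion rate can be analysed as change under SAP 6.6, and protocol 13.2.8 already plans change summaries for all efficacy endpoints. Only preference fails. Even there, a patient's proportion of hard choices has a change; the specified logistic GEE is what cannot use it.
- *That subgroup and full-sample estimates would be on different scales.* The units are the same. With baselines balanced in expectation, the treatment difference has the same expected value for change and for the Week 8 value. What differs is the response, its precision and its sensitivity to chance baseline imbalance.
- *That the change score wastes a known share of the patients.* The ratios of 1.67 to 1.18 are against a baseline-adjusted comparator that the main PRT and completion analyses do not contain. Against the planned visit value, the effect could be a loss or a gain.
- *That this split is the only planned look at the reward tasks by anhedonia.* SAP 15.2.3.10 also fits SHAPS and DARS scores as variables of interest for preference.

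It can also be said that a baseline covariate goes beyond repairing the conflict, since the Week 8 value in the existing ANOVAs would suffice. That is correct as a minimum. The covariate is still worth having: it is at least as precise as either alternative under the variance model above, apart from the degree of freedom spent. The data are already collected, and the second FERT model in SAP 15.2.3.8 adjusts for baseline in the same way.

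**Conclusion.** The point holds as a conflict within the SAP. The 15.3.4 rule matches the main analysis for MADRS, names a response that the main analysis does not use for PRT and EEfRT completion, and cannot be executed for EEfRT preference. The sentence about dropping a term has nothing to act on in the MADRS, PRT or completion models.

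The finding for preference follows from the text and needs no assumption. The precision figures rest on equal variances and an assumed r of 0.2 to 0.7; the power figures also rest on an assumed 22 per arm and an assumed 0.5 SD effect. Severity is minor: the gap is in the pre-specification of exploratory analyses.

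**What to change.** Replace the sentence in SAP 15.3.4 with one rule per row:

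- **MADRS:** change from baseline to Week 8 by the primary MMRM.
- **PRT and EEfRT completion:** the Week 8 value in the ANOVA of 15.2.3.9 or 15.2.3.10, with the corresponding baseline value as covariate (same block, and same stimulus where applicable). Show the full-sample result from the same model beside it.
- **EEfRT preference:** the Week 8 GEE with the base variables plus treatment, and its interaction models, within each SHAPS subgroup.

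Delete the sentence about dropping the anhedonia term.

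With the baseline covariate in a linear model, change and the Week 8 value give the same treatment difference, because subtracting baseline only shifts its coefficient by one. The adjustment therefore also removes the ambiguity over the response.

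The cost is a few lines of SAP text, one covariate degree of freedom per model and one extra full-sample table. No new data are needed, and the main PRT and completion tables can stay as planned.

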## 13 SAMPLE SIZE AND STATISTICAL METHODS

### 13.1 DETERMINATION OF SAMPLE SIZE

The sample size determination was based on the primary endpoint, change from baseline in the Investigator-administered MADRS total score, at Visit 7 (week 8). Approximately 100 patients will be randomized to either BTRX-246040 or placebo in a 1:1 allocation ratio. A sample size of 44 patients per treatment group will provide 75% power to detect a relative effect size of 0.5 on the MADRS total score, based on a two-sample t-test and a significance level of 0.10. All tests are two-sided. To account for patients who may discontinue early and be excluded from the analysis population, a sample size of approximately 50 patients per treatment group (total of 100 patients) will be randomized.

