#### 13.2.12 SUBGROUP ANALYSES

Subgroup analysis based on gender, baseline severity of anhedonia symptoms (SHAPS total score  $\leq 4$  and  $> 4$ ; also SHAPS total score  $\leq 7$  and  $> 7$ ) and baseline severity of anxiety (HAM-A total score  $< 20$  and  $\geq 20$ ) will be performed. Subgroups based on other characteristics may be considered. All subgroup analyses will be exploratory in nature.

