## 7.5. EXAMINATION OF SUBGROUPS

Subgroup analyses will be conducted as stated in the exploratory analysis sections. It should be noted that the study was not designed to detect treatment differences with high statistical power within subgroups.

The following subgroups will be assessed and described within the exploratory analysis sections:

- Gender.
- Baseline severity of anhedonia symptoms (SHAPS) score ( $\leq 4$ ,  $> 4$ ).
- Baseline severity of anhedonia symptoms (SHAPS) score ( $\leq 7$ ,  $> 7$ ).
- Baseline anxiety, as assessed by the Hamilton Anxiety Rating Scale (HAMA-A) score ( $< 20$ ,  $\geq 20$ )

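### The plan never estimates how the treatment effect differs between subgroups, even for the SHAPS stratum used in randomisation, and it drops an anhedonia term that no stated model contains

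*SAP*

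**What the plan says.** SAP 15.3.4 states that each listed endpoint "will be analyzed using the same method as the endpoint in the main analysis". The table that follows lists MADRS total score by gender, SHAPS ≤4/>4, SHAPS ≤7/>7 and HAM-A <20/≥20, and PRT and EEfRT by SHAPS ≤7/>7 only.

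For MADRS the main method is the MMRM of SAP 15.1.3 (Protocol 13.2.8.1): treatment, site, visit, treatment-by-visit and baseline MADRS. The covariate list in SAP 7.1 names no other interaction with treatment and has no SHAPS factor. For PRT and EEfRT the methods are the ANOVA and GEE models of SAP 15.2.3.9 and 15.2.3.10. In the GEE series, treatment and SHAPS are separate variables of interest, and each interacts only with the reward variables.

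SAP 15.3.4 adds: "For the anhedonia severity subgroup analysis, that term will be dropped from the model".

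SHAPS ≤4/>4 is the stratification factor for randomisation (Protocol 10.3). SAP 6.5 labels a result significant at 10% a trend, and SAP 7.4 declines any multiplicity adjustment. Both documents give caveats. Protocol 13.2.12 says "All subgroup analyses will be exploratory in nature", and SAP 7.5 notes that "the study was not designed to detect treatment differences with high statistical power within subgroups".

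**The concern.** The useful question in a subgroup analysis is whether the effect differs between the levels, and by how much. The plan produces an estimate and a p-value within each level and no estimate of the difference. A p-value below 0.10 in one level and above it in the other is not evidence of a difference, because two halves of a small trial will often fall on opposite sides of a threshold when the effect is the same in both. The study title names patients with or without anhedonia, and randomisation is stratified on SHAPS, so readers will look at this contrast first.

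The second problem is textual. A programmer told to drop the anhedonia term will find none in the specified models. It is then unclear whether the sentence is left over from something else or whether the main model was meant to carry the stratum.

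**Working it through.** **Inputs**

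- Protocol 13.1: "A sample size of 44 patients per treatment group will provide 75% power to detect a relative effect size of 0.5", "based on a two-sample t-test and a significance level of 0.10. All tests are two-sided". That is 88 evaluable patients.
- Protocol 13.1: "a sample size of approximately 50 patients per treatment group (total of 100 patients) will be randomized". The implied loss is 1 − 44/50 = 12%.
- Threshold for a trend: p<0.10 (SAP 6.5).
- Share of patients in each SHAPS stratum: not given. Assumed 50:50, with a range to 80:20. The 37:63 case uses the only anhedonia rate cited in the Protocol introduction, which is not tied to a SHAPS cut of 4.

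**Step 1. The plan's own figure.** Noncentrality = 0.5 × √(44/2) = 2.345 on 86 df. Power is 75.2% by noncentral t (75.8% by the normal approximation). This reproduces the stated 75%.

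**Step 2. Power within a stratum.** With n per arm in the stratum, noncentrality = 0.5 × √(n/2) on 2n − 2 df. For n = 22 this is 1.658 on 42 df, giving 49.5%.

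**Step 3. Chance that exactly one stratum reaches p<0.10 when the true effect is 0.5 SD in both.** The strata contain different patients, so the chance is pA(1 − pB) + pB(1 − pA). At 50:50 it is 2 × 0.495 × 0.505 = 0.500.

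| Split | n per arm | Power | Exactly one | Both | Neither |
|---|---|---|---|---|---|
| 50:50 | 22 / 22 | 49.5% / 49.5% | 50.0% | 24.5% | 25.5% |
| 37:63 | 16.3 / 27.7 | 40.2% / 57.7% | 51.5% | 23.2% | 25.3% |
| 30:70 | 13.2 / 30.8 | 34.8% / 61.6% | 53.5% | 21.4% | 25.0% |
| 20:80 | 8.8 / 35.2 | 26.5% / 66.7% | 57.9% | 17.7% | 24.5% |

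A simulation of 200,000 trials at 22/22 gave 50.0%. At a 5% threshold the range over these splits is 46–53%. With 100 evaluable patients it is 50–59% at the 10% threshold.

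**Step 4. No effect in either stratum.** 2 × 0.10 × 0.90 = 18% per split.

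**Step 5. The direct test.** The standard error of the between-stratum difference, in SD units, is √(2/nA + 2/nB). At 22/22 it is √(4/22) = 0.426.

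- A test at two-sided 10% gives a false contrast in 10% of trials by construction (simulated 10.0%).
- Half-width on 84 df: 1.663 × 0.426 = 0.71 SD at 90%, and 1.989 × 0.426 = 0.85 SD at 95%.
- Power at 50:50 is 32% for a true difference of 0.5 SD and 75% for 1.0 SD. At 80:20 it is 24% and 59%.
- For 75% power at a 0.5 SD difference, about 4 × 88 = 352 evaluable patients would be needed.

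**Step 6. All four MADRS splits together.** This was simulated with 20,000 trials, assuming gender and HAM-A at 50:50 and nested SHAPS cuts at 40:60 and 60:40. At least one split shows a trend in exactly one half in about 81% of trials with a uniform 0.5 SD effect, and in about 40% with no effect. At least one of four interaction tests falls below 0.10 in about 32% of trials. If the tests were independent the figure would be 1 − 0.9⁴ = 34%.

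**Step 7. The dropped term.** SAP 7.1 lists baseline score, treatment, pooled site, visit and treatment-by-visit. SAP 15.1.3 lists the same kinds of term, with baseline MADRS as the covariate. Neither has an anhedonia term, so 15.3.4 removes something that is not there. The instruction to drop a term for the anhedonia subgroups makes sense only if the model is refitted within each level, and this is the basis for inferring separate fits.

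**The case against.** The strongest reply is that the information is not lost. The main method reports the LS-mean difference with a 95% confidence interval as well as a p-value (SAP 15.1.3), and the two levels of a split contain different patients. A reader can subtract the estimates and combine their standard errors. This stands: a reader might infer that the trial cannot say whether the effect differs, but what is missing is a prespecified output.

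Several other points also stand.

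- **Separate models** are inferred. The SAP does not use those words.
- **Anhedonia as the main subgroup question.** No stated objective asks whether the MADRS effect differs by anhedonia. The secondary objective treats anhedonia as an outcome. The title may simply describe who is eligible, and stratification also serves balance.
- **Use of the p-values.** Nothing in the SAP tells the reader to compare subgroup p-values, and nothing ties them to selecting patients for a later trial. A reader might infer a wrong enrichment decision, but the documents do not support that.
- **Multiplicity.** Under no effect, at least one of the eight MADRS subgroup p-values falls below 0.10 in roughly 41–44% of simulated trials, depending on assumed prevalences. That is multiplicity, which SAP 7.4 openly leaves unadjusted and which an interaction term does not remove.
- **Model size in half the data.** The SAP has safeguards: a heterogeneous autoregressive fallback (15.1.3) and pooling or removal of site (7.1).

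The exploratory label and the power caveat lower the weight of the point but do not answer it. SAP 7.5 warns of low power within subgroups. It does not say that two p-values are not a test of a difference, and the trend label in SAP 6.5 invites that comparison.

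**Conclusion.** The point holds as an inexpensive improvement to an exploratory analysis, together with one textual conflict that needs correcting. No between-subgroup estimate is planned for any factor, including the randomisation stratum. If subgroup p-values are read against each other, a single split gives a misleading contrast in about one trial in two when the effect is a uniform 0.5 SD, and in about 18% when there is no effect. A direct test at 10% gives one in about 10%. It would be too strong to call a trend in one half only the expected result: at 50:50 it is a coin flip, with the remainder shared almost equally between both halves and neither.

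The figures rest on the protocol's t-test framework, 88 evaluable patients and an assumed stratum split. An MMRM with baseline and site would change them somewhat. They show how a p-value comparison behaves and do not show that the primary analysis is affected.

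**What to change.** In SAP 15.3.4:

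1. For MADRS, fit one MMRM per factor on the whole FAS, adding subgroup, subgroup-by-visit, treatment-by-subgroup and treatment-by-subgroup-by-visit. Report the Week 8 between-subgroup difference with its confidence interval, and take the within-subgroup contrasts from the same model.
2. For PRT and EEfRT by SHAPS ≤7/>7, an MMRM does not apply. Add the matching treatment-by-subgroup term to the ANOVA and GEE models.
3. State that subgroup p-values will not be compared with each other, and that a non-significant interaction does not show equal effects.
4. Reconcile the sentence on the dropped term with SAP 7.1 and 15.1.3, either by deleting it or by adding the SHAPS stratum to the main model. Adding the stratum changes the primary model, so SAP 3.3, which declares no changes from the protocol, would need to say so.

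The cost is SAP wording and modest programming, with no new data. The drawback is imprecision: the interval will usually be too wide to settle the question, and the four MADRS interaction tests remain unadjusted for multiplicity. Both should be stated with the results.
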